### Purpose and Study Background

Interstitial cystitis/ bladder pain syndrome (IC/BPS) is a chronic, debilitating bladder disease characterized by suprapubic pressure or pain accompanied by urinary frequency and urgency, in the absence of an identifiable cause. Population based studies have demonstrated a prevalence rate of 3 to 12 percent among women and 2 to 4 percent for men. The symptoms of IC/BPS result in a poor quality of life with sleep dysfunction, sexual dysfunction, depression, anxiety, and stress.

The pathogenesis of IC/BPS is undefined. Treatments of IC/BPS have been empirical and inadequate. Narcotics are the most commonly prescribed medication. The direct cost of medical care for IC/BPS patients is > \$11,000 per year. There are also the indirect costs to society including work absenteeism and decreased productivity. Investigation of novel therapies is needed.

IC/BPS has been postulated to be one of the autoimmune diseases. Like autoimmune diseases, IC/BPS affects more women than men. Infection and stress worsen both conditions. Pregnancy improves symptoms for both IC/BPS and autoimmune diseases. There is a clinical concordance of IC/BPS with other established autoimmune diseases. IC/BPS as an autoimmune disease is not a new theory. In 1938 Fister recognized the clinical and histopathologic similarities between IC/BPS and lupus erythematosus. In the 1980 review article, Oravisto viewed IC/BPS as an autoimmune disease due to the very chronic course of the disease, the absence of infection, the pathological findings, the common occurrence of antinuclear antibodies, and the response to certain modalities of treatment. In Immunosuppressive drugs including methotrexate, prednisone, and cyclosporine A, routinely used to treat autoimmune diseases, have shown efficacy in selected IC/BPS patients. There are more than 80 different documented autoimmune diseases affecting every organ and tissue in the body. IC/BPS may be the autoimmune disease of the bladder.

Selective release of tumor necrosis factor-alpha (TNF $\alpha$ ) by mast cells (MC) plays a central role in the pathogenesis and pathophysiology of IC/BPS. Bladder biopsies of patients with IC demonstrate increase numbers of MC. A selective release or degranulation of vasoactive and proinflammatory mediators by MC, a process called "activation", may explain IC/BPS pathogenesis. MC activation elicits an inflammatory response in urothelial cell IC/BPS models with secreted product TNF $\alpha$  playing a central role. Inflammation in experimental IC/BPS was mediated by TNF $\alpha$ . Drugs that inhibited TNF $\alpha$  decreased this experimental IC/BPS bladder inflammation. Interruption of mast cell activation, with a decrease expression of TNF $\alpha$ , inhibited bladder inflammation in an autoimmune cystitis model.

Elevated levels of TNFα in urine, serum, and tissue were found in patients with IC/BPS. TNFα, a proinflammatory cytokine released by immune cells, is central to the acute and chronic inflammation in autoimmune diseases.  $^{32,33}$  Patients with clinically diagnosed IC/BPS, but no glomerulations observed with cystoscopy under anesthesia after hydrodistention, had elevated levels of TNFα in urine or bladder wash fluid.  $^{34}$  However, patients with clinically diagnosed IC/BPS, but did have glomerulations observed with cystoscopy under anesthesia after hydrodistention, did not have elevated levels of TNFα in urine or bladder wash fluid compared to controls. Interestingly, cystoscopic findings were not felt to identify distinct subgroups of patients with IC/BPS symptoms. TNFα was upregulated in urine of patients with overactive bladder a syndrome that has been considered a milder form of IC/BPS. Serum levels of TNFα were significantly higher in patients with IC/BPS. Tissue levels of TNFα were significantly elevated in women with vulvar vestibulitis. Vulvar vestibulitis, also known as vulvodynia is part of the symptom complex in women with IC/BPS. TNFα is highly expressed in bladder urothelium tissue of patients with ulcerative IC/BPS and was suggested to be the causative etiology of IC/BPS.

I recently completed a study (ClinicalTrials.gov Identifier NCT01295814) "A Randomized, Double-Blind, Placebo Controlled Trial of Adalimumab in the Treatment of Interstitial Cystitis/Bladder Pain Syndrome". Adalimumab is one of several biological agents that are known as TNFα antagonists or TNFα blocking agents. Adalimumab is a recombinant, fully human, monoclonal antibody that neutralizes human TNFα. In this study adalimumab treatment demonstrated a statistically significant improvement in outcome measures compared to baseline in patients with moderate to severe IC/BPS. However, adalimumab failed to demonstrate positive proof of concept compared to placebo due to a significant placebo effect. This confounding result was evaluated and analyzed in my paper "Examination of the Significant Placebo Effect in the Treatment of Interstitial Cystitis/ Bladder Pain Syndrome". The

conclusions of this paper were that this greater "placebo effect" represented the benefits of advice, support, education, and behavior modification programs. The recommendation was that physicians should review standard advice with all IC/BPS patients before starting medical therapy or clinical trials. Future studies should include a washout period after subjects receive standard IC/BPS advice. Only those patients who do not improve with standard IC advice and therapy would be participants in clinical trials.

Current understanding of the TNF $\alpha$  blocking agents recognizes differences in each of their mechanism of action and clinical experience. Adalimumab may not theoretically be the best TNF $\alpha$  blocking agent for the treatment of IC/BPS. Adalimumab mediates complement-dependent cytotoxicity and antibody-dependent cell-mediated cytotoxicity. Adalimumab increases the proportion of cells undergoing apoptosis and the level of granulocyte degranulation.  This may not be therapeutically beneficial as IC/BPS histologically demonstrates a pancystitis with mast cell infiltration.  A total degranulation of these inflammatory cells with the release of histamine, cytokines, and proteolytic enzymes, typical of an anaphylactic reaction, may exacerbate bladder inflammation.

Certolizumab pegol (Cimzia) has some advantages over other TNF $\alpha$  blocking agents for the treatment of IC/BPS including better distribution in inflamed tissue, development of low levels of neutralizing autoantibodies, greater affinity to TNF $\alpha$ , and efficacy when used in monotherapy. Patients with rheumatoid arthritis treated with certolizumab pegol demonstrated a rapid clinical response, often within 2 weeks. Certolizumab pegol inhibits cytokine production. Certolizumab pegol has a unique mechanism of action that should be beneficial in the treatment of IC/BPS in that it has no complement-dependant cytotoxicity and antibody-dependant cell-mediated cytotoxicity. IC/BPS histologically demonstrates a pancystitis with mast cell infiltration. The polyethylene glycol moiety of certolizumab pegol inhibits mast cell degranulation. TNF $\alpha$  blocking agents that do not cause cytolysis and prevents degranulation of these inflammatory cells should be therapeutically beneficial in the treatment of IC/BPS.

Most trials in IC/BPS use a patient-reported global response assessment (GRA) such as "Compared to when you began this trial, how would you rate your IC symptoms now?" as the primary endpoint. The O'Leary-Sant Interstitial Cystitis Symptom Index and Problem Index (OSPI) questionnaire evaluates overall symptoms in IC/BPS patients. The OSPI results confirm the clinical diagnosis of IC/BPS and establish the severity of the participants IC/BPS baseline symptoms. The Interstitial Cystitis Symptom Index (ICSI) is one of the two O'Leary-Sant Interstitial Cystitis Symptom and Problem Indexes. ICSI has been validated as a reliable

and responsive measure of changes in IC/BPS symptoms. ICSI is recommended as an endpoint in IC clinical trials.

Research has searched unsuccessfully for an inflammatory urine biomarker for the diagnosis of IC/BPS. However, Felson demonstrated elevated urine TNF $\alpha$  levels measured by ELISA in patients with IC/BPS compared to controls. It would be interesting to measure urine TNF $\alpha$  levels with modern techniques in IC/BPS patients and see if those levels go down with certolizumab pegol treatment.

The FDA asked for more outcome measures so ICPI and numeric rating scale for pain and urgency was added. They asked for monitoring of patient with outcome data to week 18. We also agreed to change the potential total number of patients from 44 to 42 as this would maintain the 2:1 study medication ratio.

Condition	Intervention	Phase
Cystitis, Interstitial	Biological: Certolizumab pegol (Cimzia)	Phase III
Bladder Pain Syndrome	Other: Placebo	

Study Type: Interventional

Study Design: Randomized, Double-Blind, Placebo Controlled Treatment, Efficacy Study

### **Primary Outcome Measures**

The primary endpoint is improvement in global response assessment (GRA) at week 2

### **Secondary Outcome Measures**

Improvement in GRA at week 4, 10, and 18

Improvement in the Interstitial Cystitis Symptom Index (ICSI) Interstitial Cystitis Problem Index (ICPI) from baseline to week 2, 4, 10, and 18

11-point numeric pain and urgency scale at baseline, week 2, 4, 10, and 18

Midstream first void urine specimen level of TNF $\alpha$  normalized to urinary creatinine, at week 2,

4, 10, and 18 compared to baseline levels

Adverse events from time of Screening through the last clinic and phone call visit

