# **Estimated enrollment** 42 patients

After subjective evaluation of efficacy and safety in the initial 30 patients, the total study sample size will be 42 study patients.

Previous IC/BPS studies demonstrated an approximate 20% placebo response rate. Monotherapy response rate of certolizumab pegol in rheumatoid arthritis was 45%. To achieve an 80% power using 2:1 randomization and a 2-sided p = .05 a minimum of 39 subjects was required. The sample size was increased by 3 subjects to account for potential participant withdrawals.

Arms	Assigned Intervention					
Group 1: Experimental	Biological: Certolizumab pegol (Cimzia) 400 mg pre-filled syringe loading dose given subcutaneously at week 0, 2, and 4 followed by a maintenance dose at week 8					
Group 2: Placebo Comparator	Placebo: given subcutaneously at week 0, 2, 4, and week 8					

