### **Study Design**

Patients enter a one month Screening period to assess inclusion/exclusion criteria, sign informed consent, and determine study eligibility. At the initial screening visit, patients will be instructed in behavior modification techniques to improve IC/BPS symptoms.  Patients are reassessed at least one month later for inclusion/exclusion criteria and determine study eligibility. Patients who do not improve with standard IC/BPS advice and pass clinical and laboratory screening can be participants in the study. Baseline evaluation of the included patients will be done with the O'Leary-Sant Interstitial Cystitis Symptom Index and Problem Index (OSPI). At the baseline visit (week 0), all eligible IC/BPS patients will be randomized in a blinded fashion to receive in a 2:1 ratio either SQ certolizumab pegol 400mg or SQ placebo at weeks 0, 2, 4 followed by a maintenance dose at 8 weeks. The length of the study will be 18 weeks. The effectiveness of certolizumab pegol will be assessed at week 2, 4, 10, and 18 using GRA, ICSI, ICPI, and the numeric pain and urgency scale. After subjective evaluation of efficacy and safety in the initial 30 patients, the total study sample size will be 42 study patients.

A midstream urine will be collected at baseline and weeks 2, 4, 10, and 18 from all participants. Quest Diagnostics Nichols Institute, San Juan Capistrano, CA or similar lab will perform an ELISA TNFα and creatinine levels on these samples.

Pilot Study Evaluating the Efficacy of CZP for Interstitial Cystitis Study Flow Chart

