# **Trial Schedule**

	Screen	>One Month Reevaluation	Baseline	Visit 1	Visits 2, 3	Visit 4	Phone Follow- up 	Phone Follow- up 
Study Day	-37	-7	0	14	28,56	70	98	126
Study Week	-5	-1	0	2	4,8	10	14	18
Study								
procedures:								
Obtain Informed Consent	X							
Medical History	X							
Medication Review	X	X	X	X	X	X		
Vitals 	X	X	X	X	X	X		
Physical Exam	X							
OSPI 	X	X						
anti-HCV, HBsAG		X						
PPD		X						X
CBC						X		X
Urinalysis	X	X	X	X	X	X		
Urine Culture		X	X	X	X	X		
Urine Pregnancy Test		X						
Eligibility Assessment	X	X						
Dispense Study Drug			X	X	X			
Injection Site Evaluation 			X	X	X			
Adverse Events			X	X	X	X	X	X
GRA 				X	X	X		X
ICSI, ICPI 				X	X	X		X
Numeric scale of pain and urgency	X	X	X	X	X	X		X

- 1. Height, weight, blood pressure, pulse, temperature
- 2. O'Leary-Sant Interstitial Cystitis Symptom Index and Problem Index
- 3. Monitor subjects for systemic and local hypersensitivity reactions for one hour after injection

- 4. Global response assessment
- 5. Interstitial Cystitis Symptom Index, Interstitial Cystitis Problem Index
- 6. In-office visit if determined to be clinically necessary

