Statistical Analysis Plan

Pilot Study Evaluating the Efficacy of Certolizumab Pegol for Interstitial

Sample size

Previous IC/BPS studies demonstrated an approximate 20% placebo response rate [29]. Monotherapy response rate of certolizumab pegol in rheumatoid arthritis was 45% [21]. To achieve an 80% power using 2:1 randomization and a 2-sided $p = .05$ a minimum of 39 subjects was required. The sample size was increased by 3 subjects to account for potential participant withdrawals.

Randomization

Eligible participants were computer randomized and received either subcutaneous certolizumab pegol 400gm or placebo (sterile saline) in a 2:1 ratio at weeks 0, 2, 4, and 8. The study drug and placebo were provided in ready to use syringes that were identical other than the blinded ID number on the side of the syringe.

Statistical analysis

Any patient who withdrew from the study, for whatever reason, was classified as a non-responder.

All statistical summaries and 2-sample t-tests were performed using the Data Desk® version 6.3. Comparison of these changes between treatment groups are also shown as 95% confidence intervals (CI). The chi-square test or Fisher's exact test was applied to analyze baseline demographics, improvement with GRA treatment responders, and the proportion of patients with a reduction from baseline of 30% or greater in their pain intensity score between treatment groups.

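### Pain and urgency are scored twice between the advice and the first dose, but the day -7 score has no role in the efficacy analysis; averaging it with day 0 is a cheap, optional gain in precision for secondary outcomes

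*Protocol*

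**What the plan says.** The Protocol's Secondary Outcome Measures name the "11-point numeric pain and urgency scale at baseline, week 2, 4, 10, and 18". Study Design fixes the visit: "At the baseline visit (week 0), all eligible IC/BPS patients will be randomized in a blinded fashion". The Trial Schedule has a Baseline column at day 0.

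The schedule row "Numeric scale of pain and urgency" is marked at three pre-dose visits: Screen (day -37), Reevaluation (day -7) and Baseline (day 0). Study Design gives the advice at the first of these: "At the initial screening visit, patients will be instructed in behavior modification techniques to improve IC/BPS symptoms". Of the second it says: "Patients are reassessed at least one month later for inclusion/exclusion criteria and determine study eligibility".

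The Statistical Analysis section, worded alike in the Protocol and the SAP, plans two-sample t-tests, 95% confidence intervals for between-group differences in change, and a comparison of "the proportion of patients with a reduction from baseline of 30% or greater in their pain intensity score between treatment groups". Neither document states which pre-dose score is the baseline for these analyses, and neither gives the day -7 pain or urgency score a part in them.

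**The concern.** The day -7 and day 0 scores both describe the patient after the advice and before any study drug. A single 0-10 rating of a fluctuating symptom is usually noisy, and noise in the baseline score passes straight into the change from baseline. With 42 patients split 2:1 there are 14 on placebo, so precision is scarce. A second reading of the same untreated state is already scheduled and appears to go unused.

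At stake is the precision of the change comparisons for pain and urgency, which are secondary outcomes. The word baseline also needs pinning down. For the O'Leary-Sant indexes the last pre-dose assessment in the Trial Schedule is at day -7, so the schedule does not tie baseline to day 0 for every scale.

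**Working it through.** **The plan's own figures.** None exists for this scale: no SD, correlation, effect size or power is stated. The only design figure, the minimum of 39 subjects, concerns response rates and does not enter here.

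**Inputs.** From the documents: scores at day -7 and day 0, follow-up at weeks 2, 4, 10 and 18, 42 patients (14 placebo, 28 active), two-sided 0.05. Assumed: equal SD at all times (set to 1), rb = correlation of day -7 with day 0, and r0 and r7 = correlations of day 0 and day -7 with follow-up.

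**Change-score variance.**
- Day 0 only: 2(1 - r0).
- Mean of the two: 1 + (1 + rb)/2 - (r0 + r7).
- If r0 = r7 = r, the proportional reduction is (1 - rb)/[4(1 - r)].

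| rb | r | Reduction |
|---|---|---|
| 0.7 | 0.7 | 0.3/1.2 = 25% |
| 0.7 | 0.5 | 0.3/2.0 = 15% |
| 0.8 | 0.3 | 0.2/2.8 = 7% |
| 0.9 | 0.5 | 0.1/2.0 = 5% |
| 0.95 | 0.3 | 0.05/2.8 = 1.8% |

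Whenever rb is at least r, 25% is the ceiling. It is reached only when all three correlations are equal.

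**With covariate adjustment.** The residual variance is 1 - r² with day 0 alone and 1 - r²/[(1 + rb)/2] with the mean. At r = 0.5, rb = 0.7 this is 0.750 against 0.706, a 6% reduction. At r = rb = 0.7 it is 17%; at r = 0.3, rb = 0.9 it is 0.5%.

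**If correlation fades with time.** Day 0 is then closer to follow-up than day -7 is. The reduction in variance is (1 - rb)/2 - (r0 - r7), as a share of 2(1 - r0), so it vanishes once r0 - r7 reaches (1 - rb)/2.
- Weekly first-order autoregression, no measurement noise, autocorrelation 0.80 to 0.95: the mean raises week-2 variance by 4 to 10% and saves 0 to 5% at week 18.
- The same with measurement noise, reliability 0.7 to 0.9 and autocorrelation 0.90 to 0.98: the mean saves 4 to 22% over the four planned weeks, and loses at none of them.

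**What it buys.** At 14:28 and 80% power, the detectable difference in SDs of the day-0 change score is (1.960 + 0.842) × √(1/14 + 1/28) = 0.917. Multiplying by √(1 - reduction) gives 0.908 at 2%, 0.845 at 15% and 0.794 at 25%. Equivalently, power of 80% becomes about 81%, 86% and 90%.

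**The 30% pain criterion.** Simulated patients with no true change, assuming mean pain 5.5, between-patient SD 1.5, within-patient SD 1 or 2 and integer scores from 0 to 10. The table gives the proportion falsely meeting the criterion.

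| Baseline used | SD 1 | SD 2 |
|---|---|---|
| Day 0 only | 11% | 26% |
| Mean, day -7 not inflated | 9% | 23% |
| Mean, day -7 inflated by 0.5 point | 12% | 25% |
| Mean, day -7 inflated by 1 point | 14% | 28% |

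**The case against.** Taking the last score before the first dose as baseline is conventional, valid and unbiased. Averaging is a refinement, and its size rests on correlations that the documents do not give. If correlation fades quickly and ratings carry little noise, the simple mean loses precision at week 2. Day -7 is also a selection visit: the first exclusion criterion removes patients whose symptoms were relieved by then, so the scores of those who remain may be selectively high.

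Much of this stands:
- A reader might infer that a fixed share of variance, such as 7 to 25%, is certainly being lost. The documents do not support that. The range belongs to one set of assumed correlations, and values near 2% are reachable.
- A reader might infer that averaging will reduce false 30% responders. The simulation shows that modest inflation at day -7 can cancel or reverse that gain.
- A reader might infer that the plan expressly restricts baseline to day 0. It does not; this is the natural reading of two sections taken together.

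Two parts carry less weight. The loss at week 2 needs a single rating almost free of measurement noise, which is unlikely for one 0-10 item. Selection at day -7 precedes randomisation, so it affects both arms alike: it can enlarge change within each arm but does not bias the comparison between them.

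**Conclusion.** The point holds as an inexpensive improvement of optional priority. Two post-advice, pre-dose scores are scheduled, and the natural reading uses one. Averaging would probably lower change-score variance by somewhere between 2 and 25%, with 15% at r = 0.5 and rb = 0.7, and by about 0 to 17% under covariate adjustment. These figures assume equal variances and equal correlation of the two baseline scores with follow-up; with fading correlation the gain persists if single ratings carry ordinary measurement noise.

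It would be too strong to call the present plan wrong or biased, or to say the trial's main conclusion is at risk. The primary endpoint, GRA at week 2, uses no baseline score and is untouched. The benefit is confined to the pain and urgency scales among the secondary outcomes, and no benefit should be claimed for the 30% pain criterion.

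**What to change.** In the Protocol's Secondary Outcome Measures and the SAP's Statistical analysis section, define baseline pain and baseline urgency for the between-arm change analyses as the mean of the day -7 and day 0 scores, using the single available score if one is missing. Leave out day -37, which precedes any effect of the advice. If a covariate-adjusted model is adopted, enter both scores as covariates instead; the data then set their weights, which also deals with fading correlation. State which baseline the 30% pain criterion uses, and report a day-0-only version as a sensitivity analysis.

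The cost is a few sentences in the plan and one extra analysis, with no added visit or assessment. The drawback is that within-arm change may look somewhat larger if day -7 scores are selectively high, so within-arm figures should be read with that in mind.

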# **Estimated enrollment** 42 patients

After subjective evaluation of efficacy and safety in the initial 30 patients, the total study sample size will be 42 study patients.

Previous IC/BPS studies demonstrated an approximate 20% placebo response rate. Monotherapy response rate of certolizumab pegol in rheumatoid arthritis was 45%. To achieve an 80% power using 2:1 randomization and a 2-sided p = .05 a minimum of 39 subjects was required. The sample size was increased by 3 subjects to account for potential participant withdrawals.

Arms	Assigned Intervention					
Group 1: Experimental	Biological: Certolizumab pegol (Cimzia) 400 mg pre-filled syringe loading dose given subcutaneously at week 0, 2, and 4 followed by a maintenance dose at week 8					
Group 2: Placebo Comparator	Placebo: given subcutaneously at week 0, 2, 4, and week 8					

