### **Statistical Analysis**

All statistical summaries and 2-sample t-tests were performed using the Data Desk® version 6.3. Comparison of these changes between treatment groups are also shown as 95% confidence intervals (CI). The chi-square test or Fisher's exact test was applied to analyze baseline demographics, improvement with GRA treatment responders, and the proportion of patients with a reduction from baseline of 30% or greater in their pain intensity score between treatment groups.

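### The stated 80% power at 39 subjects is wrong: for 45% vs 20% at 2:1, the planned two-arm test has about 29% (Fisher) to 34% (chi-square) power

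*Protocol*

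**What the plan says.** The protocol section on estimated enrollment and the SAP section on sample size give the same rationale. The placebo assumption is: "Previous IC/BPS studies demonstrated an approximate 20% placebo response rate". The active assumption is borrowed from another disease: "Monotherapy response rate of certolizumab pegol in rheumatoid arthritis was 45" per cent. The protocol then concludes: "To achieve an 80% power using 2:1 randomization and a 2-sided p = .05 a minimum of 39 subjects was required". The SAP repeats the figure and adds the withdrawal allowance: "a minimum of 39 subjects was required. The sample size was increased by 3 subjects to account for potential participant withdrawals". At 2:1, 39 is 26 active and 13 placebo, and 42 is 28 and 14. Neither document names the formula, the software or the test behind the 39.

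The primary endpoint is GRA improvement at week 2 (protocol, Primary Outcome Measures). Both documents give the test: "The chi-square test or Fisher's exact test was applied to analyze baseline demographics, improvement with GRA treatment responders", with the comparison made between treatment groups. The SAP alone adds: "Any patient who withdrew from the study, for whatever reason, was classified as a non-responder". Both also promise 95% confidence intervals for changes between groups, without saying whether the GRA responder difference is one of those changes.

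**The concern.** A difference of 25 percentage points, with an active rate near one half, usually needs well over 100 subjects at 2:1 for 80% power, so 39 looks far too small. The stated power decides how a non-significant result is read. At 80%, a null result is moderate evidence against an effect of the assumed size. At about one third, it says very little. The protocol's background reports that the preceding adalimumab trial failed to separate from placebo, so a null result is a realistic prospect here.

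**Working it through.** **Inputs.** Placebo rate 0.20, active rate 0.45, 2:1 allocation, two-sided 0.05, 80% power and N = 39 come from the sample-size text of both documents. The test is chi-square or Fisher's exact (Statistical Analysis, both documents).

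**Step 1: try to reproduce 39 as a two-group calculation.** Pooled normal formula, with n = placebo arm and 2n = active arm:

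n = [z(0.975)·√(1.5·p̄(1−p̄)) + z(0.80)·√(p0(1−p0) + p1(1−p1)/2)]² / (p1−p0)²

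- p̄ = (0.20 + 2×0.45)/3 = 0.3667, so √(1.5×0.2322) = 0.590
- √(0.16 + 0.12375) = 0.533
- n = (1.960×0.590 + 0.842×0.533)² / 0.0625 = 2.576/0.0625 = 41.2
- Total = 123.7 unrounded, or 42 + 84 = 126 in whole patients

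Other two-group versions do not reach 39 either:

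| Version | Total N |
|---|---|
| Two-sided 2:1, unpooled variance | 107 to 108 |
| Two-sided 2:1, arcsine | about 120 |
| Two-sided 2:1, continuity-corrected | 144 |
| Two-sided 1:1, pooled | 108 |
| One-sided 2:1, pooled | 99 |
| One-sided 1:1, unpooled (smallest found) | about 82 |

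**Step 2: find what does give 39.** Take an exact one-sample binomial test of the active arm against a fixed 20%. At n = 26 the critical count is 10 responders: P(X ≥ 10 | 0.20) = 0.0232 and P(X ≥ 10 | 0.45) = 0.806. This is the first n with at least 80% power at an upper tail of 0.025, and 26 × 1.5 = 39. Neither document describes such a test, so this origin is an inference.

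**Step 3: power of the planned test.** Power is the sum, over all pairs (a, b) with p ≤ 0.05, of Bin(a; n1, 0.45) × Bin(b; n0, 0.20).

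| Active/placebo | Fisher | Chi-square, uncorrected | Chi-square, Yates |
|---|---|---|---|
| 26/13 | 29.3% | 33.6% | 18.8% |
| 28/14 | 33.2% | 37.9% | 22.1% |

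The normal approximation at 26/13 agrees: Φ[(0.25√13 − 1.157)/0.533] = Φ(−0.479) = 31.6%.

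**Step 4: total N for 80% by exact power at 2:1.** Fisher gives 79.8% at 132 and 81.1% at 135. Uncorrected chi-square gives 79.4% at 120 and 80.8% at 123.

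**Step 5: withdrawals.** Suppose 3 of the 42 withdraw and are scored as non-responders. With an assumed split of 2 active and 1 placebo, Fisher power at 28/14 is 29.3%. It is 22.5% if all three are active and 45.5% if all three are placebo. The documents do not give the split.

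**Step 6: what 42 subjects can show.**

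- Active rate detectable with 80% power against 20% (Fisher): about 65%, or about 68% with the 2 + 1 withdrawals.
- With 3/14 placebo responders (21%), significance needs 16/28 active (57%) with Fisher or 15/28 (54%) with chi-square.
- A result close to plan, 13/28 vs 3/14, gives Fisher p = 0.18 and chi-square p = 0.12.
- Wald 95% CI if exactly 45% and 20% were observed: 0.25 ± 1.96·√(0.45×0.55/28 + 0.20×0.80/14) = 0.25 ± 1.96×0.142, or −3 to +53 points.

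**The case against.** The strongest reply is that 39 is not an arithmetic slip. It matches the one-sample calculation in Step 2, so the fault would be a mismatch between sizing method and analysis. That may well explain the number, and the sponsor should state the method used. It does not rescue the claim. A one-sample test treats the placebo rate as known, whereas the plan estimates it from 13 or 14 patients, and the protocol itself blames a large placebo effect for the earlier trial's failure.

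The SAP title calls this a pilot, and between-group confidence intervals are planned. A pilot may be small, but the protocol also labels the trial a Phase III efficacy study, and both documents state 80% outright.

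The withdrawal figures deserve caution. The primary endpoint is at week 2 of an 18-week study. If patients leave later and their observed week-2 GRA stands, power at 28/14 stays at 33% to 38%. The SAP rule read literally scores every withdrawal as a non-responder, but it does not address timing. That qualifies Step 5 and leaves Step 3 untouched.

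Naming Fisher is partly a preference. With both true rates at 20% and 28/14, its actual type I error is 2.9%, against 4.6% for uncorrected chi-square. Either test can be defended. Leaving the choice open cannot, because at 15/28 vs 3/14 Fisher gives p = 0.057 and chi-square p = 0.047.

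**Conclusion.** The concern holds and must be fixed. At the plan's own rates, allocation and significance level, the stated minimum of 39 gives 29% (Fisher) to 34% (uncorrected chi-square) power, not 80%. The planned 42 gives 33% to 38%, and 80% would take about 135 or 123 subjects respectively. Neither document corrects the figure.

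The result rests on the two stated rates being the design assumptions and on the described between-arm test being the primary analysis. The 42-subject figures assume that no withdrawal affects the week-2 outcome. The lower figures with withdrawals depend on an assumed split and on those patients counting as non-responders at week 2.

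**What to change.** In the protocol (estimated enrollment) and the SAP (sample size), delete the 80% claim, state how the 39 was obtained, and name one test for the primary endpoint. Suggested text, with Fisher as the example:

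> With 42 subjects (28:14) and Fisher's exact test at two-sided 0.05, power is about 33% for 45% vs 20%. Power of 80% is reached only for an active rate of about 65% against 20%. Withdrawals counted as non-responders may lower these figures (for example, to about 29% power if 2 active and 1 placebo subject withdraw; assumed split).

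If uncorrected chi-square is named instead, the corresponding power is about 38%.

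In the analysis text of both documents, say explicitly that the 95% confidence interval covers the week-2 GRA responder difference, and that a non-significant result will be interpreted from that observed interval.

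**Cost.** The change is wording in two documents and adds no patients. The stated power becomes much less favourable, and choosing Fisher over chi-square gives up about 5 points (33.2% vs 37.9%). The protocol mentions the agreed total of 42 alongside the FDA's requests, so the corrected rationale may also have to be explained there. Keeping the 80% claim at these rates would instead mean roughly tripling the sample, to about 123 to 135.
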